We would also be like to assess the burden and natural history of those oral cancer patients reporting to us who might have taken treatments from outside and had not received any standard oral care due to reasons mentioned in the protocol. We will be comparing their findings separately with our two experimental groups. This will help to highlight the importance of having a standard oral care protocol for all patients of oral cancer. Further it will provide us with information about the status of oral health in patients who have not received any preventive and supportive oral care as a part of their cancer treatment.

The objectives of this study are.

1. To compare the impact of two professional fluoride application regime on DMFT index among patients with oral & oro-pharyngeal cancer.
2. To validate, pilot test, document and standardize institutional oral care protocol for all patients of oral & oro-pharyngeal cancer.

2. Hypothesis

H0: There will be no difference in outcome between two professional fluoride application regimes regarding defined parameters in patients of oral & oro-pharyngeal cancer.

H1: Fluoride application regime with monthly professional application will have better outcome as compared to four monthly application in cancer patients regarding defined parameters.

3. Methods:

Objective 1: To compare the impact of two fluoride application regime on DMFT index among oral cancer patients.

Study design: Randomized controlled trial & observation design

After completion of pilot study, validation of institutional oral care protocol this study will start. The study will be a prospective Randomized controlled trial with parallel groups. Intervention group will be receiving monthly professional fluoride application and control group will be receiving four monthly professional fluoride application. Each group will further be divided in to two subgroups with either gel application or varnish application. The groups will be compared for DMFT index to compare the effectiveness of the fluoride application regime at 4 time points (0,1,6,12 months). The study will be conducted at Cancer research institute, Swami Rama Himalayan University, Dehradun (CRI, SRHU). All new cases of oral cancer receiving treatment will be enrolled.

Inclusion criteria:

1. Patient with histopathological diagnosis of squamous cell carcinoma of oral cavity & oro-pharynx.
2. Patient aged 18 years and above
3. More than 10 teeth in oral cavity
3. Gives consent

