Evaluation: Patients will be evaluated for set parameters at baseline, one month after completion of primary treatment, six month and one year after completion of cancer treatment. There will be no blinding of any kind. The patients will be kept on recall

for longer period to study effect on the oral health parameters but this will not be part of the present study.

Sample size: Present study will be a prospective randomized parallel group study with allocation ratio of 1:1. As there is no previously available data on frequency of fluoride application as proposed by us. We assume that fluoride monthly application will result in 60 % reduction in decay and quarterly application will result in 30 % reduction in decay at end of 1 year observation period. New patients with established diagnosis of oral cancer will be enrolled as per protocol. Sample of 60 patients in each group (intervention and control) is planned at 1% alpha and 90% power 95% confidence interval.

Sample size calculation:

$$n = \{Z_{1-\alpha/2} \sqrt{P_1(1-P_1)} + Z_{1-\beta} \sqrt{P_2(1-P_2)}\}^2 / (P_1-P_2)^2$$

$$n = 54$$

We assume that monthly professional monthly fluoride application with standard oral care protocol will improve oral health and quality of life parameters by 60 % and Four monthly professional fluoride standard oral care protocol will improve oral health and quality of life parameters 30 % at one year after completion of the study. We will be considering taking 20% as attrition rate (20% of 54 = 10.8, rounded to 11);

The final sample size will be 66patients per group. (Subdivided in 33 patients in gel and varnish group)

The annual load of oral cancer reported at CRI SRHU is approximately 200. We will be randomly recruiting 66 cases in both groups. Each group will be further divided into two subgroups to receive either gel or varnish application.

Statistical analysis: The data will be collected and entered in MS excel 2010. Different statistical analysis will be performed using SPSS software version 22. Intention to treat analysis will be used for the analysis of data.

Trial evaluation and follow up:

The data will be evaluated on 6 monthly duration for adherence to set protocol with information to institutional ethical committee board.

Trial stopping rules:

The clinical trial will be stopped for any of the following reasons.

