Once the validity is established, pilot testing will be initiated and will include patients of oral cancer reporting to oncology OPD at CRI.

Sample size: The pilot study will be done for 10 consecutive patients (15% of sample size of randomized trial) and will be complete in one-month time frame.

Evaluation: Compliance of the patients with the oral care regime and their feedbacks will be documented. The pilot will also be used as an opportunity to probe into any potential hindrance in conduct of the study. Any problem identified will be addressed and resolved before starting the randomized trial.

Consent: A written informed consent of all the patients will be taken, patients will be informed that they are a part of pilot study and their data is being used to pilot the randomized trial. They will not be part of the aforementioned randomized trial.

Ethical considerations: The patients enrolled in the pilot study will receive the oral care protocol intervention and all the potential benefits if any.

To standardize institutional oral care protocol, after completion of piloting and validation we will observe the two arms of randomized trial participants for a year at 0,1,6,12 month period for quality of life and oral health indicators. (Defined in operational definition). (Observation design)

To document the effect of insufficient oral supportive care and its effect on oral health and quality of life, we would enroll patients who could not receive oral care for any reasons and will document their oral health status. Patients will be enrolled by total enumeration technique and these patients will be provided all supportive oral care once they come in our contact. (Observation design)

We will also estimate load and pattern of oral cancer cases reporting to Cancer research institute, Swami Rama Himalayan University. After obtaining the ethical clearance, acceptance of protocol by university and necessary permission from central

records this study will start. It will be the collection of retrospective data of number and type of oral cancer patients reported to CRI, SRHU in last 8 years. This will be done to document load and pattern of oral cancer in our region. The number of patients will be as per our central record database (2011-2018). Necessary permission will be taken for assessing the records. (Historical design retrospective)

4. Major expected findings and significance of the findings

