The present study is conducted to standardized oral care module and assess the effect of two different professionally fluoride application regime on the outcome variable such as oral health indicators and quality of life in oral cancer patients.

Oral care is the most neglected aspect of care in oral cancer treatment in India due to various reasons ranging from economical burden on patients to lack of integration of dental care in cancer treatment at majority of cancer treatment centers. There is a critical need of devising and providing oral care as basic standard of care for oral cancer patients.

Proposed outcome

1. Standardization and documentation of our institutional oral care protocol for cancer patients.
2. Effect of monthly versus four monthly professionally applied fluoride regime on defined outcomes of oral & oro-pharyngeal cancer patients
3. Efficiency and comparison of Varnish and gel type of fluoride professional application.
4. Identification of oral care and treatment needs in cancer patients.

5. Formulation of an economical oral care module for recourse limited countries and assessing oral care economical burden.
6. Integration of dental care services in oncology treatment as an essential supportive care for oral & oro-pharyngeal cancer patients.
7. Inclusion of dental oncology expert as a part of oncology cares team for oral & oro-pharyngeal cancer patients.
8. Documentation of prevalence and pattern of oral & oro-pharyngeal cancer in our region.

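### Proposed outcome 8 promises regional prevalence and pattern, but a count of patients reporting to one institute gives only that institute's caseload and case mix

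*Protocol*

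**What the plan says.** Three statements in the protocol bear on this point.

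- **Section 4, Proposed outcome, item 8:** "Documentation of prevalence and pattern of oral & oro-pharyngeal cancer in our region".
- **Section 3, Methods for Objective 2, opening sentence of the record-review paragraph:** "We will also estimate load and pattern of oral cancer cases reporting to Cancer research institute, Swami Rama Himalayan University".
- **Same paragraph, on source and purpose:** the work is a "collection of retrospective data of number and type of oral cancer patients reported to CRI, SRHU in last 8 years", followed by "This will be done to document load and pattern of oral cancer in our region". The source is the institute's central record database for 2011–2018, and the paragraph labels the design as historical and retrospective.

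For scale, the sample-size text under Objective 1 says "The annual load of oral cancer reported at CRI SRHU is approximately 200". Neither of the two numbered objectives mentions prevalence.

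**The concern.** The target changes between the start of the record-review paragraph and the list of outcomes. It begins as cases reporting to the institute, becomes the load and pattern of oral cancer in the region, and ends as regional prevalence. The data source is the same throughout.

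Prevalence is the number of people living with a disease in a defined population, divided by the size of that population. A list of patients who presented to one centre supplies neither term. The word pattern has a related difficulty: the mix of cancer types seen at one institute describes the region only if the institute sees all of the region's cases or a representative share, and the protocol says nothing about that share.

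At stake is what the study may conclude from this component. If item 8 is reported as worded, a hospital count would be presented as a regional epidemiological figure that the data cannot support.

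**Working it through.** **1. The protocol's own figure.** The record window is given as the last 8 years and as 2011–2018. Counting both end years, 2018 − 2011 + 1 = 8. The two statements agree. The protocol gives no prevalence figure to reproduce.

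**2. What the stated method can produce.** The input is about 200 oral cancer cases a year (Objective 1, Sample size).

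Caseload = annual load × years = 200 × 8 = 1,600 patients.

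This assumes that the approximate present load applied in every year from 2011, which the protocol does not say.

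**3. What item 8 would need, against what the protocol supplies.**

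| Needed for a regional prevalence | In the protocol |
|---|---|
| A defined region or catchment | Not given |
| The size of its population | Not given |
| The share of regional cases seen at CRI, or a registry or survey that covers the region | Not given |
| The number of people living with the disease at a point in time | Not given; the source counts patients who reported over a period |

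The numerator is of the wrong kind and there is no denominator, so no prevalence can be computed.

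**4. Does the count at least fix a regional rate of new presentations?** This needs two figures that the protocol lacks. As an illustration, assume a catchment population of 1 to 10 million, a share of regional cases seen at CRI of 20% to 100%, and all CRI patients resident in that catchment.

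Rate per 100,000 per year = 200 / (share × population) × 100,000

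- Share 20%, population 1 million: 200 / (0.2 × 1,000,000) × 100,000 = 100
- Share 100%, population 10 million: 200 / (1.0 × 10,000,000) × 100,000 = 2

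The same 200 cases a year fit anything from 2 to 100 per 100,000, a 50-fold range. Even a value inside that range would be a rate of presentation and not a prevalence. The range reflects the assumptions chosen. It shows that the count does not determine the regional quantity, and it does not estimate an error.

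**5. The wording side by side.** The opening sentence of the record-review paragraph (cases reporting to the institute) matches the data. The later sentence in that paragraph (in the region) and item 8 (prevalence in the region) do not.

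**The case against.** The strongest reply is that this is a loose word and not a flaw in method. The operative sentence in the Methods already states the right target, and nothing there converts the count into a prevalence. Someone who follows the Methods will obtain the number and type of patients at CRI. Item 8 is the last line of a list of expected findings, next to aspirations such as adding a dental oncology expert to the team, and it is not a trial endpoint.

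Most of this stands. It makes the point minor and shows that the correct wording is already in the protocol. It does not remove the point. Item 8 names something that the study is to document, and no other data source is offered for it. Reading prevalence loosely as burden would still leave the regional claim, which the same Methods paragraph repeats. Nor could a later analysis plan supply a denominator that the data source does not contain.

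A reader might infer more than the documents support:

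- **That the protocol shows regional cases being missed.** The background mentions "oral cancer patients reporting to us who might have taken treatments from outside". Those patients do report to CRI and would be in its count, so the sentence is no evidence of missed cases.
- **That the count includes referrals from outside the region.** This is plausible, but the protocol does not say where patients come from.
- **That a stage distribution or a time trend would mislead.** The paragraph plans number and type only. It mentions neither stage nor a trend analysis.
- **That the error has a known size or direction.** Any such figure would rest on assumed coverage, disease duration and constant load, none of which the protocol gives.

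**Conclusion.** Item 8 is wrong as written, and the point is minor. A retrospective count from one institute cannot give the prevalence of oral and oro-pharyngeal cancer in a region, and it cannot be taken to give the regional pattern. It does give the institute's caseload and case mix, and that part remains deliverable.

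The conclusion rests on the absence from the protocol of any catchment, population denominator, regional case source or count of living cases. It does not depend on the illustrative rates. No numerical error can be attached to it. The 1,600 is a rough caseload under constant load, and no figure in the protocol is shown to be false.

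It would be wrong to read this as a weakness of the trial itself. The record review is separate from the randomised comparison, the DMFT outcome and the sample size, and none of these changes.

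**What to change.** 1. In section 4, reword proposed outcome 8 to: *number and type of oral and oro-pharyngeal cancer patients reporting to CRI, 2011–2018*.
2. In the Methods for Objective 2, replace the phrase placing the load and pattern in the region with *among patients reporting to CRI*, so that the paragraph agrees with its own opening sentence.
3. State that each patient is counted once over the 8 years.
4. Make no prevalence or regional claim from these data.

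The cost is two short wording changes, a check for repeat entries when the records are extracted, and a narrower claim. No new data are needed. If a regional prevalence is wanted, it would take a defined population and a population-based source of living cases, which would be a different study component.
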